7.1.2. Adverse Event Severity

Adverse events are graded by the investigator as Grade 1, 2, 3, or 4 using the Gilead Grading Scale for Severity of Adverse Events and Laboratory Abnormalities. The severity grade of events for which the investigator did not record severity will be categorized as “missing” for tabular summaries and data listings, and the most severe will be considered (for sorting purpose only) in data presentation.

7.1.3. Relationship of Adverse Events to Study Drug

Related AEs are those for which the investigator selected “Related” on the AE eCRF to the question of “Related to Study Treatment.” Events for which the investigator did not record the relationship to study drug will be considered to be related to study drug for summary purposes. However, by-subject data listings will show the relationship as missing from that captured on the eCRF.

7.1.4. Serious Adverse Events

Serious adverse events (SAEs) will be identified and captured as SAEs if AEs met the definitions of SAE specified in the study protocol. Serious adverse events captured and stored in the clinical database will be reconciled with the SAE database from the Gilead Drug Safety and Public Health Department before database finalization.

7.1.5. Treatment-Emergent Adverse Events

7.1.5.1. Definition of Treatment-Emergent

Treatment-emergent adverse events (TEAEs) are defined as one or both of the following:

- Any AEs with an onset date on or after the study drug start date and no later than 30 days after permanent discontinuation of study drug
- Any AEs leading to premature discontinuation of study drug.

7.1.5.2. Incomplete Dates

If the onset date of an AE is incomplete, then the month and year (or year alone if month is not recorded) of onset determine whether an AE is treatment emergent, as long as the AE stop date is not prior to the first dose date of study drug. The event is considered treatment emergent if both of the following 2 criteria are met:

- The AE onset and end dates are the same as or after the month and year (or year) of the first dose date of study drug
- The AE onset date is the same as or before the month and year (or year) of 30th day after the date of the last dose of study drug

An AE with completely missing onset and stop dates, or with the onset date missing and a stop date later than the first dose date of study drug, will be considered to be treatment-emergent.

7.1.6. Summaries of Adverse Events and Deaths

A brief high-level summary of TEAEs will be provided for the “SOF/VEL 12 Weeks” group for the number and percentage of subjects who had the following: any AE, any AE of Grade 3 or above, any AE of Grade 2 or above, any treatment-related AE, any treatment-related AE of Grade 3 or above, any treatment-related AE of Grade 2 or above, any SAE, any treatment-related SAE, any AE that led to premature discontinuation of SOF/VEL, any AE that led to interruption of SOF/VEL. All deaths (including those that are treatment emergent and those that are not treatment emergent) observed during the study will also be summarized and included in this table.

Adverse event summaries will provide the number and percentage of subjects with TEAEs by SOC and PT, for the “SOF/VEL 12 Weeks” group based on the Safety Analysis Set as follows:

- All AEs
- AEs of Grade 3 or above
- AEs of Grade 2 or above
- All treatment-related AEs
- Treatment-related AEs of Grade 3 or above
- Treatment-related AEs of Grade 2 or above
- All SAEs
- All treatment-related SAEs

Multiple events will be counted once only per subject in each summary. Adverse events will be summarized and listed first in alphabetic order of SOC and then by PT in order of descending incidence within each SOC. In summaries by severity grade, the most severe grade will be used for those AEs that occurred more than once in an individual subject during the study.

In addition to the above summary tables, TEAEs will be summarized by PT only, in order of descending incidence for:

- AEs that occurred in at least 5% of subjects within any treatment group
- AEs of Grade 3 or above
- AEs related to study drug
- All SAEs
- AEs leading to premature discontinuation of study drug
- AEs leading to interruption of study drug

In addition to the summaries described above, data listings will be provided for the following:

- All AEs (with a variable indicating whether the event is treatment emergent)
- AEs of Grade 3 or above
- SAEs
- Deaths
- AEs leading to premature discontinuation of study drug

7.2. **Laboratory Evaluations**

Laboratory data collected during the study will be summarized using both quantitative and qualitative methods. Summaries of laboratory data will be provided for the Safety Analysis Set and will include data collected up to the last dose date of study drug plus 30 days. The analysis will be based on values reported in conventional units. When values are below the limit of quantitation, they will be listed as such, and the closest imputed value will be used for the purpose of calculating summary statistics. For example, if “< 50” was recorded, a value of 49 will be used for the purpose of calculating summary statistics; if “< 0.1” was recorded, a value of 0.09 will be used for the purpose of calculating summary statistics. Hemolyzed test results will not be included in the analysis, but they will be listed in by-subject laboratory listings.

For this study, an enzymatic serum creatinine test was used (reflex test) when the sample was icteric and serum creatinine level could not be determined by the central laboratory. Results from

the enzymatic serum creatinine test will be used in place of a missing serum creatinine value per the standard methodology, when appropriate. Covance Laboratories has conducted correlation testing to show that the results of these 2 tests are similar and can be pooled for analysis.

A by-subject listing for laboratory test results will be provided by subject ID number and visit in chronological order for hematology, serum chemistry, and urinalysis separately. Values falling outside of the relevant reference range and/or having a severity grade of 1 or higher on the Gilead Grading Scale for Severity of Adverse Events and Laboratory Abnormalities will be flagged in the data listings, as appropriate.

No inferential statistics will be generated.

7.2.1. Summaries of Numeric Laboratory Results

Descriptive statistics (n, mean, SD, median, Q1, Q3, minimum, and maximum) will be provided for the “SOF/VEL 12 Weeks” group for ALT, aspartate transaminase (AST), total bilirubin, alkaline phosphatase, hemoglobin, reticulocytes, white blood cells (WBC), neutrophils, lymphocytes, platelets, and international normalized ratio (INR) as follows:

- Baseline values
- Values at each postbaseline visit
- Change from baseline at each postbaseline visit

A baseline laboratory value will be defined as the final assessment performed on or prior to the date of first dose of study drug. Change from baseline to a postbaseline visit will be defined as the visit value minus the baseline value. The mean, median, Q1, Q3, minimum, and maximum will be displayed to reported number of digits, SD to reported number of digits plus 1.

Median (Q1, Q3) of the observed values for ALT, AST, total bilirubin, alkaline phosphatase, hemoglobin, reticulocytes, WBC, neutrophils, lymphocytes, and platelets will be plotted using a line plot for the “SOF/VEL 12 Weeks” group by visit.

In the case of multiple values in an analysis window, data will be selected for analysis as described in Section 3.8.3 (Selection of Data in the Event of Multiple Records in a Window).

The percentage of subjects with at least 1 postbaseline (up to 30 days post last dose) hemoglobin value < 10 g/dL and < 8.5 g/dL will be summarized for the “SOF/VEL 12 Weeks” group. The denominator will be the number of subjects with at least 1 postbaseline hemoglobin value. Note that a subject with a minimum hemoglobin value on treatment of 8.3 g/dL would be counted in both categories.

A listing of subjects meeting the criteria for postbaseline hemoglobin < 10 g/dL and < 8.5 g/dL will be provided.

7.2.2. **Graded Laboratory Values**

The Gilead Grading Scale for Severity of Adverse Events and Laboratory Abnormalities will be used for assigning toxicity grades (0 to 4) to laboratory results for analysis. Grade 0 includes all values that do not meet the criteria for an abnormality of at least Grade 1. Some laboratory tests have criteria for both increased and decreased levels; analyses for each direction (ie, increased, decreased) will be presented separately.

7.2.2.1. **Treatment-Emergent Laboratory Abnormalities**

Treatment-emergent laboratory abnormalities are defined as values that increase at least 1 toxicity grade from baseline at any postbaseline time point, up to and including the date of last dose of study drug plus 30 days. If the relevant baseline laboratory value is missing, then any abnormality of at least Grade 1 will be considered treatment emergent.

7.2.2.2. **Summaries of Laboratory Abnormalities**

Laboratory data that are categorical will be summarized using the number and percentage of subjects in the study with the given response at baseline and each scheduled postbaseline visit.

The following summaries (number and percentage of subjects) for treatment-emergent laboratory abnormalities will be provided for the “SOF/VEL 12 Weeks” group by analyte; subjects will be categorized according to the most severe postbaseline abnormality grade for a given analyte:

- Graded laboratory abnormalities
- Grade 3 or above laboratory abnormalities

For all summaries of laboratory abnormalities, the denominator is the number of subjects with nonmissing postbaseline values up to 30 days after last dose for the laboratory parameter of interest.

A by-subject listing of treatment-emergent Grade 3 or above laboratory abnormalities will be provided by subject ID number and visit in chronological order. This listing will include all test results that were collected throughout the study for the analyte of interest, with all applicable severity grades or abnormal flags displayed. By-subject listings of laboratory data will be provided by subject ID number and visit in chronological order.

7.3. **Body Weight, Height, and Vital Signs**

Vital signs (systolic and diastolic blood pressure [mmHg], and pulse [beats/min]) at each visit, and change from baseline at each visit will be summarized for the Safety Analysis Set using descriptive statistics (n, mean, SD, median, Q1, Q3, minimum, and maximum) for the “SOF/VEL 12 Weeks” group. The baseline value will be defined as the last available value collected on or prior to the date of first dose of study drug. Change from baseline to a postbaseline visit will be defined as the postbaseline value minus the baseline value.

In the case of multiple values in an analysis window, data will be selected for analysis as described in Section 3.8.3 (Selection of Data in the Event of Multiple Records in a Window). No inferential statistics will be generated.

A by-subject listing of body weight, height, BMI, and vital signs (systolic and diastolic blood pressure [mmHg], pulse [beats/min], respiration [breaths/min], and body temperature [°C]) will be provided by subject ID number and visit in chronological order.

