Most HCV drug development efforts have been focused on GT1 HCV infection as this is the most prevalent HCV genotype in developed countries {Gower et al 2014}. However, over half of all HCV infections are non-GT1: estimates from 2 recent meta-analyses indicate GT3 HCV is the next most common accounting for 22-30% of infections, while GT2 and GT4 each account for approximately 8 to 13%, GT6 for approximately 2 to 5%, and GT5 for approximately 1% of HCV infections worldwide. Among patients with liver transplantation, non-GT1 HCV infections are also high. In the US, about 20% of HCV infections among liver transplant recipients are non-GT1 {Campos-Varela et al 2015, Lim 2015}. In Spain, approximately 15% of HCV infections among patients with liver transplants are non-GT1 (10% GT1a, 75% GT1b, 2% GT2, 5% GT3, and 5% GT4){Forns et al 2003}. The number of non-GT1 HCV infections is even higher in other countries that perform liver transplantation, and reflects the country specific background prevalence's of HCV genotypes. In the United Kingdom, 40% of HCV infections among patients with liver transplants are GT3, 40% of HCV infections are non-GT-1 among Korean liver transplant recipients, and 45% are non-GT1 among Australia and New Zealand liver transplant recipients){Kim et al 2016, Zekry et al 2003}. The availability of a well-tolerated, all oral, ribavirin-free, short duration therapy such as SOF/VEL that is effective across all HCV genotypes would be a major advance for the treatment of HCV infection globally. This is particularly true for patients with liver transplants who often have reduced blood cell counts or GFRs at baseline, making them susceptible to ribavirin-associated toxicities. There are no approved ribavirin-free regimens for these patients, regardless of genotype

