#### **4.3. Exclusion Criteria**

Subjects who meet *any* of the following exclusion criteria are not to be enrolled in this study:

- 1) Multi-organ transplant that includes heart or lung recipient (patients who have their liver transplant as part of a liver-kidney dual transplant are eligible to enroll)
- 2) Subjects with de novo or recurrent Hepatocellular Carcinoma (HCC) posttransplant

- 3) Current use of corticosteroids at any dose >5mg of prednisone/day (or equivalent dose of corticosteroid)
  - 4) Child-Pugh-Turcotte (CPT) Score >7 at Screening
  - 5) Recipient of ABO incompatible organ
  - 6) Histological evidence of unresolved rejection
  - 7) Infection with hepatitis B virus (HBV) or human immunodeficiency virus (HIV) at Screening
  - 8) Current, uncontrolled ascites, variceal hemorrhage, hepatic encephalopathy, hepatorenal syndrome, hepatopulmonary syndrome, or other signs of decompensated cirrhosis
  - 9) Serum creatinine >2.5x upper limit of normal (ULN) or stage 4 chronic kidney disease (CrCl <30ml/min)
  - 10) Screening ECG with clinically significant abnormalities
  - 11) Subjects with the following laboratory results at Screening are excluded unless enrollment is approved by the sponsor medical monitor
    - ALT, AST or alkaline phosphatase >10 x ULN
    - Direct bilirubin  $\geq 4$  x ULN
    - WBC <2,000/mm^3\*
    - ANC <1,000cells/mm^3\*
    - Platelets <50,000/mm^3\*
    - HbA1C >8.5%
    - Hemoglobin <9g/dL\*
- \*Use of GM-CSF, epoetin alfa or other therapeutic agents to increase cell counts for the purposes of meeting eligibility criteria is prohibited.
- 12) Use of GM-CSF, epoetin alfa or other therapeutic agents within 2 weeks of Screening
  - 13) History of other clinically relevant chronic liver disease (e.g., hemochromatosis, autoimmune hepatitis, Wilson's disease,  $\alpha$ -1-antitrypsin deficiency, alcoholic liver disease, non-alcoholic steatohepatitis, or toxin exposure)
  - 14) Recent (within 4 weeks of Screening) episode or infection requiring systemic antibiotics

- 15) Use or planned use of T-cell depleting/masking antibodies, systemic antineoplastic agents, cyclosporine >300mg/day, or use of any prohibited medications listed in Section 5.4 within 28 days of the Baseline/Day 1 visit
- 16) Prior exposure to any HCV NS5A inhibitor

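### The postbaseline hemoglobin <10 g/dL table ignores baseline although subjects may enter at 9.0-9.9 g/dL, so it mixes pre-existing with new low hemoglobin

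*SAP*

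**What the plan says.** SAP 7.2.1 defines a threshold summary for hemoglobin, reported in Table 15.11.6.1.6 and supported by Listing 16.2.8.1.1: "The percentage of subjects with at least 1 postbaseline (up to 30 days post last dose) hemoglobin value < 10 g/dL", and likewise for values below 8.5 g/dL. On the denominator it says: "The denominator will be the number of subjects with at least 1 postbaseline hemoglobin value". It adds an example: "Note that a subject with a minimum hemoglobin value on treatment of 8.3 g/dL would be counted in both categories". Neither the rule nor the example uses the subject's baseline value.

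Protocol 4.3, item 11, sets the entry limit. Subjects with "Hemoglobin <9g/dL" at Screening are "excluded unless enrollment is approved by the sponsor medical monitor". So 9.0-9.9 g/dL is eligible outright, and lower values are eligible by approval. Protocol 1.1 expects low counts in this population, referring to "patients with liver transplants who often have reduced blood cell counts or GFRs at baseline".

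Two other hemoglobin outputs do refer to baseline. SAP 7.2.1 summarizes baseline, visit values and change from baseline (Table 15.11.6.1.5). SAP 7.2.2.1 and Protocol 8.6.3 count a graded abnormality as treatment-emergent only if it is at least one grade worse than baseline (Tables 15.11.6.2 and 15.11.6.3).

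**The concern.** The reporting threshold (10 g/dL) lies above the entry limit (9 g/dL), so a subject can meet the table's criterion before the first dose. A reader will naturally take the percentage as a measure of anemia arising on the regimen, and part of the trial's rationale is to avoid ribavirin in patients whose counts are already low. Without a control arm, nothing in the table shows how much of the percentage was there at entry. For that use the error runs one way: subjects already low at entry can only raise the count.

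**Working it through.** There is no planned figure to reproduce here, so the check applies the SAP rules to example subjects and then sizes the effect.

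**Inputs**
- Threshold rule (SAP 7.2.1): counted if the minimum postbaseline hemoglobin, up to 30 days after last dose, is <10 g/dL; likewise for <8.5 g/dL.
- Treatment-emergent rule (SAP 7.2.2.1): worst postbaseline grade is higher than the baseline grade.
- Grades (Protocol Appendix 3, HIV-negative adults; HIV is an exclusion): Grade 1, 10.0-10.9 g/dL or a fall of 2.5 to <3.5; Grade 2, 9.0 to <10.0 or a fall of 3.5 to <4.5; Grade 3, 7.0 to <9.0 or a fall of >=4.5; Grade 4, <7.0.
- Planned N = 80 (SAP 1.2).

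**Step 1. The SAP's example.** A minimum of 8.3 g/dL is counted under both thresholds, as the SAP states.

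**Step 2. Other subjects**

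| Baseline (g/dL) | Postbaseline (g/dL) | Counted <10? | Fell below baseline? | Treatment-emergent grade? |
|---|---|---|---|---|
| 9.5 | 9.5 throughout | yes | no | no (Grade 2 before and after) |
| 9.0 | 9.3 to 9.9 | yes | no, it rose | no |
| 9.5 | 10.1 throughout | no | no | no |
| 10.2 | one value of 9.9 | yes | yes | yes (Grade 1 to 2) |

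The first two are counted with no decline. The third shows that entering at 9.0-9.9 g/dL does not by itself lead to being counted: at least one postbaseline value must be below 10.

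**Step 3. Size.** Each subject who is below 10 at baseline and counted adds 1/80 = 1.25 percentage points. The documents give no baseline distribution, so the following rests on assumption: 4 subjects fall from >=10 to <10 g/dL, and k others are below 10 at baseline and stay there.

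| k | SAP rule, (4+k)/80 | Baseline >=10 only, 4/(80-k) |
|---|---|---|
| 0 | 5.0% | 5.0% |
| 1 | 6.25% | 5.1% |
| 2 | 7.5% | 5.1% |
| 4 | 10.0% | 5.3% |
| 8 | 15.0% | 5.6% |

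**Step 4. Do the other outputs supply the missing number?** Anyone who goes from >=10 to <10 g/dL moves from Grade 0 or 1 to at least Grade 2, so all new cases are among the treatment-emergent Grade 2 or higher subjects. That group also holds others. A fall from 14.0 to 10.4 is 3.6 g/dL, hence Grade 2 without going below 10. A fall from 9.6 to 8.6 is Grade 2 to Grade 3 in someone already below 10. The graded table therefore gives an upper limit, not the new-onset count. Means, quartiles and minima by visit do not link a low postbaseline value to that subject's baseline.

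**Step 5. The 8.5 g/dL threshold.** It lies below the 9 g/dL entry limit. A baseline below 8.5 can occur only through medical monitor approval or a fall between Screening and first dose.

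**The case against.** The strongest reply is that the table is accurate for what it is titled. It describes postbaseline values, does not call them treatment-emergent, and drives no endpoint, stopping rule or test; Protocol 8.1.2 names a different primary safety endpoint (an AE leading to permanent discontinuation). Baseline hemoglobin is summarized with its minimum, so a reader can see whether anyone started below 10. Worsening is reported in the graded tables, and the by-subject hematology listing gives values by visit. The threshold table and the graded table do not contradict each other: one reports level, the other worsening. All of this stands, and it limits the consequence. What it does not supply is a tabulated count of subjects newly below 10 g/dL.

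A second reply concerns the remedy. Limiting the table to subjects with baseline >=10 g/dL would remove the subject who falls from 9.6 to 8.6 g/dL: no longer in the <10 count, and not below 8.5. That would hide a real decline in the subjects with least reserve. This also stands, and it is why the overall count should stay.

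A reader might go further and infer that this is the trial's main anemia result and that it will overstate anemia on SOF/VEL by some definite amount. The documents do not support that. Nothing gives the table that status, and the general remark in Protocol 1.1 about reduced blood counts says nothing on how many subjects will enter below 10 g/dL.

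**Conclusion.** The point holds as a modest flaw in one descriptive safety table and its listing. The <10 g/dL percentage combines subjects already low at baseline with those who became low, and no other planned summary separates them. Its size is 1.25 percentage points per affected subject, assuming all 80 planned subjects have a postbaseline value; the number affected cannot be stated from the documents. Entry is judged on the Screening value while baseline is the last value on or before first dose, so the two can differ. It would be wrong to infer that every subject entering at 9.0-9.9 g/dL is counted, or that the <8.5 g/dL row is affected to the same degree; steps 2 and 5 of the working show why not.

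**What to change.** In SAP 7.2.1 and Table 15.11.6.1.6:
- Keep the overall <10 and <8.5 g/dL rows as they are.
- Under <10 g/dL, add a split by baseline hemoglobin, >=10 versus <10 g/dL. The denominator of each row is the number of subjects in that baseline group with at least one postbaseline value. The first row gives the new-onset cases; the second shows those already low and removes nobody.
- Make sure Listing 16.2.8.1.1 shows the baseline value, so that further declines in the second group can be seen. Only the listing's title is available, so it may already do so.

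The data are already collected. The cost is a sentence of SAP text and one or two extra table rows. The <8.5 g/dL row needs no split.

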7.4. Prior and Concomitant Medications

Medications collected at screening and during the study will be coded using the current version of the World Health Organization (WHO) Drug dictionary. The medications will be categorized as prior or concomitant using the following definitions:

- Prior medications: any medications taken and stopped prior to or on the date of first study drug administration
- Concomitant medications: any medications taken after the date of first study drug administration and up to the last dosing date of the study drug

Concomitant medications (other than study drug and drugs administered to prevent rejection of the transplanted organ) will be summarized by Anatomical Therapeutic Chemical (ATC) drug class Level 2, and preferred name using the number and percentage of subjects for the “SOF/VEL 12 Weeks” group. A subject reporting the same medication more than once will be counted only once when calculating the number and percentage of subjects who received that medication. The summary of concomitant medications will be ordered alphabetically by ATC drug class and then by descending frequency of preferred names within an ATC drug class. For drugs with the same frequency, sorting of preferred names will be done alphabetically.

Summaries will be based on the Safety Analysis Set. No inferential statistics will be generated.

For purposes of analysis, any medication with a stop date that is on or prior to the initial study drug dosing date or start date that is after the last study drug dosing date will be excluded from a concomitant medication summary. If a partial stop date is entered, any medication with the month and year (if day is missing) or year (if day and month are missing) prior to the initial study drug dosing date will be excluded from the concomitant medication summary. If a partial start date is entered, then any medication with the month and year (if day is missing) or year (if day and month are missing) after the study drug stop date will be excluded from the concomitant medication summary. Medications with completely missing dates will be included in the concomitant medication summary.

All prior and concomitant medications (other than per-protocol study drugs and immunosuppressants given to prevent rejection of the transplanted liver) will be provided in a by-subject listing sorted by subject ID number and administration date in chronological order.

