### **5.4. Prior and Concomitant Medications**

Concomitant medications taken within 30 days of Screening, up to and including the date of the visit four weeks after discontinuation of study drug, need to be recorded in the source documents and eCRFs. All concomitant medications should be recorded in the source documents (including all blood products).

For subjects on a calcineurin inhibitor (e.g., tacrolimus, sirolimus, everolimus) for post-transplant immunosuppression, levels should be collected as per the standard schedule (or as clinically indicated) for dose management at the clinical site, and processed at the local laboratory. Management of the immunosuppression is not part of the clinical protocol, but levels and resulting dose adjustments will be recorded to assess whether the regimens required adjustment in correlation with resolution of the HCV infection.

The following medications are prohibited from 28 days prior to the Baseline/Day 1 visit through the end of study drug dosing:

- Use of corticosteroids at any dose > 5mg of prednisone/day (or equivalent dose of corticosteroid) for maintenance of immunosuppression is prohibited. However, use of steroids for the short term treatment of Acute Cellular Rejection (ACR) is up to the discretion of the Investigator.
- Investigational agents or devices for any indication

Concomitant use of certain medications or herbal/natural supplements (inducers of drug transporters i.e. P-gp) with study drug may result in pharmacokinetic interactions resulting in increases or decreases in exposure of study drug or these medication. The use of the following agents is prohibited from 28 days prior to Baseline/Day 1 through the end of study drug dosing. The use of amiodarone is prohibited from 60 days prior to Baseline/Day 1 through the end of study drug dosing.

Examples of representative medications which are prohibited or are to be used with caution are listed below:

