7.5. Concomitant Immunosuppressants

Immunosuppressant medications administered to prevent rejection of the transplanted liver will be summarized separately by Anatomical Therapeutic Chemical (ATC) drug class Level 2, and preferred name. The WHO preferred name and drug code will be attached to the clinical database. Immunosuppressants taken while the subject is receiving study drug will be summarized by WHO drug class and generic name. Definitions for concomitant medications and imputations for partial dates are as described for concomitant medications. The summary of concomitant immunosuppressant medications will be ordered alphabetically by ATC drug class and then by descending frequency of preferred names within an ATC drug class.

The number and percentage of subjects with any change in concomitant immunosuppressant medication will be summarized overall by reason for change (drug-drug interaction [DDI], protocol defined change [PDC], improvement in organ function [IOF], renal insufficiency [RIS], failing graft [FGR], and other [OTH]). The denominator for percentage calculation is the number of subjects taking any concomitant immunosuppressant for the safety analysis set. Similarly, for each drug class, the number and percentage of subjects with a dose change will be summarized by reason for change (denominator will be number of subjects receiving a concomitant drug in that class). The classes will be calcineurin inhibitors (cyclosporin, tacrolimus), rapamycin inhibitors (sirolimus, everolimus), purine/pyrimidine synthesis inhibitors (mycophenolate and its derivatives), antimetabolites (azathioprine), and corticosteroids (prednisone, prednisolone, methylprednisolone). A subject may have more than 1 reason for change recorded, and may appear in more than 1 change category.

A listing of immunosuppressant drugs administered to subjects will be provided, including the reason for any dose modification. If suspected drug-drug interaction is the reason marked for a dose change, whether the drug-drug interaction was confirmed will be included.

For subjects who take calcineurin or mTOR inhibitors (a class of drugs that inhibit the mechanistic target of rapamycin) and have blood concentrations collected, a listing will be provided. This listing will be sorted by subject ID, calcineurin or mTOR inhibitor name, and date of collection for the blood sample.

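### The summary of immunosuppressant changes inherits a last-dose cut-off and leaves out post-treatment starts, and possibly post-treatment dose changes, that the protocol collects for four more weeks

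*SAP*

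**What the plan says.** **Collection.** Protocol 5.4 has concomitant medications recorded from 30 days before Screening "up to and including the date of the visit four weeks after discontinuation of study drug". For immunosuppressants it adds a purpose: "levels and resulting dose adjustments will be recorded to assess whether the regimens required adjustment in correlation with resolution of the HCV infection".

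**Definition.** SAP 7.4 defines concomitant medications as "any medications taken after the date of first study drug administration and up to the last dosing date of the study drug". It then removes from the summary any medication with a "start date that is after the last study drug dosing date will be excluded from a concomitant medication summary".

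**Application to immunosuppressants.** SAP 7.5 imports that rule: "Definitions for concomitant medications and imputations for partial dates are as described for concomitant medications". Two summaries follow. In the first, "Immunosuppressants taken while the subject is receiving study drug will be summarized by WHO drug class and generic name". In the second, "The number and percentage of subjects with any change in concomitant immunosuppressant medication will be summarized overall by reason for change", and dose changes are also counted within each drug class. The second is Table 15.11.7.7.3. SAP 7.5 sets no separate date window for a change.

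**Listing.** SAP 7.5 also states: "A listing of immunosuppressant drugs administered to subjects will be provided, including the reason for any dose modification". This is Listing 16.2.4.4.2, and no end date is given for it.

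**Neighbouring safety summaries.** Treatment-emergent adverse events (SAP 7.1.5.1) and treatment-emergent laboratory abnormalities (SAP 7.2.2.1) run to 30 days after the last dose.

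**The concern.** The change table covers a shorter period than the data gathered for it and than the safety tables beside it, and the SAP gives no reason. The reason codes in SAP 7.5 include drug-drug interaction, improvement in organ function, renal insufficiency and failing graft. None of these need stop mattering on the day of the last tablet. If a dose was altered because of a suspected interaction, a reversal once SOF/VEL has stopped would come after the cut-off.

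Two things are at stake. First, if the reader wants the number needing a change over the whole recorded period, the table can only undercount it. A renal adverse event on post-treatment day 15 would be counted, while a new immunosuppressant started because of it would not. Second, the rule is incomplete. It acts on the start date of a medication, and the SAP does not say how a dose change within a continuing drug is dated. Two programmers could produce different versions of the same table.

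**Working it through.** The documents give no figure for the frequency of immunosuppressant changes, so there is none to reproduce. The check has three parts.

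**1. What the rule excludes**

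| Event after the last dose | In Table 15.11.7.7.3? |
|---|---|
| New immunosuppressant started | No. Its start date is after the last dose (SAP 7.4, applied by 7.5) |
| Dose change to a drug taken throughout, recorded with its own start date | No, by the same rule |
| Dose change to a drug taken throughout, held under the original start date | Not excluded by the rule; no date limit on the change is stated |

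Only the first row is settled by the text. The choice between the second and third depends on how the eCRF records a dose change, which the documents do not show.

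**2. Recorded time outside the table**

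Inputs: 12 weeks of treatment = 84 days (SAP 1.2); collection to the post-treatment Week 4 visit = 28 days, ±5 days (Protocol 5.4 and 6.3.1).

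- Share outside = 28 / (84 + 28) = 28/112 = 25%.
- With the visit window: 23/107 = 21% to 33/117 = 28%.

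Time after viral suppression: Protocol 1.2.2.1.1 to 1.2.2.1.3 reports HCV RNA below LLOQ at Week 4 in more than 88.5%, 90.2% and 91.7% of subjects in earlier SOF/VEL trials. If suppression here also comes by Week 4 (assumption), recorded post-suppression time runs from Week 4 to Week 16, which is 12 weeks. Of these, 8 are in the table and 4 are outside: 4/12 = 33%.

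**3. Subjects affected, for illustration**

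Assumptions: every post-treatment change is excluded (the second row above applies); first changes occur at a constant rate; and a proportion p of 80 subjects has a first change by Week 16, that is, post-treatment Week 4. The proportion with a first change by Week 12 is then 1 − (1 − p)^(12/16).

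| p by Week 16 | By Week 12 | Difference | Subjects of 80 |
|---|---|---|---|
| 10% | 1 − 0.90^0.75 = 7.6% | 2.4% | 1.9 |
| 20% | 1 − 0.80^0.75 = 15.4% | 4.6% | 3.7 |
| 30% | 1 − 0.70^0.75 = 23.5% | 6.5% | 5.2 |

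The table would miss about 2 to 5 subjects, or 22% to 24% of those with any change.

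**The case against.** The strongest answer is that the rule excludes medications, not changes. A maintenance immunosuppressant taken during treatment is concomitant, and SAP 7.5 puts no date on the change, so a change on post-treatment day 10 to such a drug is not expressly excluded. This stands. It leaves one clear exclusion (a drug first started after the last dose) and one undetermined case.

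A reader might infer that changes following viral clearance are dropped. The documents do not support this. If suppression follows the earlier trials, most recorded post-suppression time is on treatment and stays in the table. The protocol does not define resolution of infection. If it means SVR12, the Week 4 end of collection in Protocol 5.4 is itself too early, although Protocol 6.3.2 and Appendix 2 do schedule a concomitant-medication assessment at post-treatment Week 12.

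A reader might also infer that post-treatment changes are lost from the report. This is not supported either, because Listing 16.2.4.4.2 has no stated cut-off and may carry them with their reasons. With about 80 subjects they could be counted by hand. A listing does not, however, supply the number and percentage by reason that SAP 7.5 sets out to give.

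Immunosuppressant change is not an objective or endpoint, Protocol Section 8 specifies no analysis of it, and an on-treatment count is a legitimate quantity. These points also stand and limit the importance of the issue. They do not explain why the window is shorter than collection or settle how a change is dated. Finally, a table by reason, even when extended, does not relate changes to virologic response. The fix completes the count and goes no further.

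**Conclusion.** The point holds in a limited form and is minor. SAP 7.5 carries the last-dose cut-off into the change-by-reason table. Immunosuppressants started after the last dose are excluded, and post-treatment dose changes to a continuing drug are excluded only if each is recorded with its own start date.

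The size in time is 28 of about 112 recorded days (25%). The size in subjects, about 2 to 5 of 80, rests on three assumptions: a 10% to 30% first-change proportion by post-treatment Week 4, a constant rate, and the reading under which all post-treatment changes are excluded. The documents support none of these with data. If only newly started drugs are excluded, the number is smaller and cannot be estimated from the documents.

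The effect is confined to a descriptive safety table. SVR12, the sample size and the primary safety endpoint are untouched.

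**What to change.** In SAP 7.5 and Table 15.11.7.7.3:

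- count changes by date of change, from first dose through last dose + 30 days (or the post-treatment Week 4 visit);
- show on-treatment and post-treatment changes in separate columns, so that the on-treatment count remains visible;
- state that a dose change within a continuing drug is dated by the day of the change, whatever the start date of the drug.

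Keep the last-dose cut-off for all other concomitant medications.

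The cost is about two sentences in the SAP and one table column, using data the protocol already has sites collect. The small downside is that immunosuppressants would have a different end date from other medications, which a table footnote can state.
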